6.3.1 Duration of an Individual Patient's Study Participation

Patients may receive modakafusp alfa until they experience PD, unacceptable toxicity, or any other discontinuation criterion is met (Section 9.4). In Parts 1 and 2, the maximum scheduled duration of treatment will be 1 year; however, patients with clinical benefit can continue treatment beyond 1 year with explicit sponsor approval. Patients in the modakafusp alfa plus dexamethasone cohort can continue receiving single-agent modakafusp alfa if the investigator considers that there are clinical reasons (for example safety) supporting the removal of dexamethasone from the treatment.

Patients may be treated in Part 3 until progression or other discontinuation criteria are met. If the investigator considers that treatment after PD is in the patient's best interest, it can be approved after consultation with the sponsor.

Patients will be evaluated 30 days (EOT visit) after the last dose of modakafusp alfa or right before the start of subsequent systemic anticancer therapy to permit the detection of any delayed TEAEs.

Patient participation includes up to 21 days of screening, 1 year of treatment (Parts 1 and 2) or until disease progression (Part 3), and 1 month posttreatment follow-up (EOT visit). Patients who discontinue for reasons other than PD will continue PFS follow-up every 4 weeks from the EOT visit until the occurrence of PD, death, the start of subsequent systemic antineoplastic therapy, study termination (Section 9.4), or until 6 months after the discontinuation of study treatment, whichever occurs first. OS follow-up continues every 12 weeks from the EOT visit until death, study termination, or patient withdrawal.

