6.3.4 Total Study Duration

Patients will be followed for 30 days after the last dose of modakafusp alfa or right before the start of subsequent anticancer therapy, whichever occurs first, to permit the detection of any

delayed TEAEs. All patients, including those patients no longer on treatment, will be assessed for PFS and survival. Patients who discontinue the study treatment for any reason other than PD will be followed for PFS every 4 weeks from the EOT visit until PD, start of new systemic anticancer treatment, death, withdrawal of consent for further follow-up, study termination, or until 6 months after the discontinuation of study treatment, whichever occurs first. Patients will be followed for OS every 12 weeks from the EOT visit until death, study termination, or patient withdrawal.

Information on any subsequent anticancer therapies will be collected during the PFS/survival follow-up period. For patients who achieve CR but discontinue study treatment while still in remission, PFS information based upon available local data for Parts 1 and 2 and central data for Part 3 will also be collected during the PFS/survival follow-up period.

It is anticipated that this study will last for approximately 90 months.

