	If treatment has been held for >28 consecutive days without resolution of the toxicity (to baseline or Grade ≤1), consider permanently discontinuing study treatment unless there is clinical benefit for the patient as assessed by the investigator and with sponsor's approval.
Grade 4 AEs (except asymptomatic Grade 4 laboratory AEs)	Permanently withdraw the patient from the study, except when the investigator determines that the patient is receiving clinical benefit and has discussed this with the sponsor.

AE: adverse event; IRR: infusion-related reaction; TEAE: treatment-emergent adverse event. This table does not include guidance for the management of bleeding TEAEs, which is found in Table 8.e or for the management of IRRs, which is found in Table 8.g, Table 8.h, Section 8.7.1.1.1, and Section 8.7.1.1.2.

Potential dose modifications in Part 3 are to be discussed with the sponsor before implementation.

Table 8.d Part 3 Dose Reduction Levels

	120 mg	240 mg
1st dose level reduction	80 mg	160 mg
2nd dose level reduction	Discontinue treatment	120 mg
3rd dose level reduction	NA	Discontinue treatment

NA: not applicable.

8.4.3.3 Parts 1. 2. and 3

Table 8.e provides dose modification recommendations for bleeding TEAEs in Parts 1, 2, and 3 to mitigate the risk of fatal hemorrhagic events.

Table 8.e Parts 1, 2, and 3 Dose Modification Recommendations for Modakafusp Alfa Bleeding TEAEs

This table does not include guidance for management of IRRs. Refer to Table 8.g and Table 8.h for the management of IRRs.

Criteria	Action
Grade 1 and 2	No dose reductions or interruptions. Treat according to local practice.
Grade 3 without associated Grade 4 thrombocytopenia	Hold next infusion of modakafusp alfa until resolution to Grade ≤1 or baseline, and then resume treatment. Subsequent occurrence: Discontinue modakafusp alfa.
Grade 3 with associated Grade 4 thrombocytopenia	Discontinue modakafusp alfa.
Grade 4	Discontinue modakafusp alfa.

IRR: infusion-related reaction; TEAE: treatment-emergent adverse event.

This table does not include guidance for the management of IRRs, which is found in Table 8.g, Table 8.h, Section 8.7.1.1.1, and Section 8.7.1.1.2.

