8.7.1.1.2 Grade 3 or Higher IRRs

The recommendations for managing Grade ≥3 IRRs are presented in Table 8.h.

Table 8.h Recommendations for Managing Grade ≥3 IRRs

IRR	Action
Any Grade 4 event	Patient must be withdrawn from treatment.
Grade 3 bronchospasm or laryngeal edema	Patient must be withdrawn from treatment.
Grade 3 event other than bronchospasm or laryngeal edema	Infusion must be stopped, and the patient must be observed carefully until resolution of the IRR.
If the intensity of the IRR remains at Grade 3 after 2 hours:	Patient must be withdrawn from treatment.
If the intensity of the IRR decreases to Grades 1 or 2:	Infusion may be restarted at the investigator's discretion. Administer corticosteroids, acetaminophen, and antihistamines per Sections 8.6.1 and 8.6.2 before restarting infusion. Within 2 hours upon restart, the infusion rate should be half of that employed before the interruption. Subsequently, the infusion rate may be increased at the investigator's discretion.
If the intensity of the IRR returns to Grade 3:	The procedure described above may be repeated after restart of the infusion at the investigator's discretion.
If the intensity of the IRR increases to Grade 3 for a third time:	Patient must be withdrawn from treatment.

IRR: infusion-related reaction.

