9.4.1 Discontinuation of Treatment with Study Drug and Patient Replacement

Study drug must be permanently discontinued for patients meeting any of the following criteria:

• Patient experiences an AE or other medical condition that indicates to the investigator that continued participation is not in the best interest of the patient.

Treatment with study drug may also be discontinued for any of the following reasons:

- AE.
- Complete 1 year of treatment (unless exception is granted by the sponsor) in Parts 1 and 2 only.
- Protocol deviation (after discussion with sponsor).
- Progressive disease (if the investigator considers that treatment after PD is in the patient's best interest, it can be approved after consultation with the sponsor).
- Symptomatic deterioration.
- Unsatisfactory therapeutic response.

- Study terminated by sponsor.
- Withdrawal by subject.
- Female patient has confirmed pregnancy.
- Lost to follow-up.
- Other.

Once study drug has been discontinued, all study procedures outlined for the EOT visit will be completed as specified in the SOE (Appendix A). The primary reason for study drug discontinuation will be recorded on the eCRF.

In Part 1, patients who miss 1 or more modakafusp alfa infusions during Cycle 1 for reasons other than a DLT will be replaced. In Part 2 and Part 3, patients who receive 1 or more infusions of study drug will not be replaced.

Note that some patients may discontinue study drug for reasons other than PD before completing the full treatment course; these patients will remain in the study for posttreatment assessments as outlined in the SOE (Appendix A) until PD or withdrawal of consent.

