9.4.2 Withdrawal of Patients From Study

A patient must be withdrawn from the study for any of the following reasons:

- Lost to follow-up.
- Study terminated by sponsor.
- Withdrawal by subject.
- Completed study.
- Transfer of patient to a long-term safety study, single-patient investigational new drug application, or similar program.
- Death.
- Other.

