9.5 Posttreatment Follow-up Assessments

Patients in Parts 1 and 2 may receive modakafusp alfa for up to 1 year; however, patients with clinical benefit can continue treatment beyond 1 year with explicit sponsor approval. Patients in Part 3 may continue treatment until PD.

The PFS visits should occur every 4 weeks from the EOT visit until the occurrence of progression, death, the start of subsequent systemic antineoplastic therapy, study termination (Section 9.4), or until 6 months after the discontinuation of study treatment, whichever occurs first. OS follow-up continues every 12 weeks from the EOT visit until death, study termination, or patient withdrawal. For all patients who received study therapy and then receive subsequent anticancer therapy, next lines of therapy will be recorded, including dates of initiation and termination, regardless of whether it is initiated before or after PD. Information about disease

response/status should also be recorded. Imaging tests for patients with extramedullary disease should be performed every 12 weeks or if new symptoms suggest PD.

See the SOE (Appendix A) for appropriate assessments during follow-up.

NOTE: Treatment-related SAEs must be reported to the Global Pharmacovigilance department or designee. This includes deaths that the investigator considers related to study drug that occur during the posttreatment follow-up. Refer to Section 10.0 for details regarding definitions, documentation, and reporting of SAEs.

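### Protocol Table 8.c withdraws Part 3 patients with certain Grade 4 nonhematologic adverse events from the study, while Sections 6.3.1, 6.3.4 and 9.4.1 keep patients who stop drug in follow-up

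*Protocol*

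**What the plan says.** The row in question is the last one in Protocol Table 8.c (Section 8.4.3.2, Part 3 nonhematologic toxicities). It covers Grade 4 events except asymptomatic laboratory ones; the table also excludes bleeding and infusion-related reactions. Its action is: "Permanently withdraw the patient from the study, except when the investigator determines that the patient is receiving clinical benefit". The exception applies once the investigator has discussed it with the sponsor.

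Elsewhere the Protocol keeps patients who stop drug under observation:

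- Section 6.3.1: "Patients who discontinue for reasons other than PD will continue PFS follow-up every 4 weeks from the EOT visit".
- Section 6.3.4: "All patients, including those patients no longer on treatment, will be assessed for PFS and survival".
- Section 9.4.1 lists an adverse event as a reason to stop study drug and says of those who stop early without progression: "these patients will remain in the study for posttreatment assessments as outlined in the SOE (Appendix A) until PD or withdrawal of consent".
- Section 9.5 repeats the four-weekly PFS visits and adds: "OS follow-up continues every 12 weeks from the EOT visit until death, study termination, or patient withdrawal".

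Leaving the study has its own section, 9.4.2, which opens: "A patient must be withdrawn from the study for any of the following reasons". No adverse event is on its list, although the list ends with a residual category, Other.

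**The concern.** A site that applies the row as written would close the patient's participation, whereas Sections 6.3.1, 6.3.4 and 9.4.1 require it to continue. The data at risk are assessments made after drug is stopped. The SAP relies on them: the Part 3 primary estimand (SAP 5.3.4) handles treatment discontinuation by a treatment policy strategy, and SAP 7.8.2.1 counts assessments made after discontinuation towards the response rate. Under SAP Table 1, a patient who leaves without confirmed progression or death is censored for PFS at the last adequate assessment. Here the departure would be caused by severe toxicity, so the censoring could not be assumed to be unrelated to outcome.

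**Working it through.** The plan gives no figure on this point, so the check is mainly a comparison of texts.

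**1. What the patient leaves, by place in the Protocol**

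| Place | Situation | Patient leaves |
|---|---|---|
| Table 8.c, Grade 4 row | Nonhematologic event, Part 3 | The study |
| Table 8.c, row above | Grade 3 or asymptomatic Grade 4 laboratory event, held more than 28 days | Study treatment (to be considered) |
| Table 8.a | Life-threatening Grade 4 event, Parts 1 and 2 | The study (to be considered), then text on restarting treatment |
| Table 8.e | Grade 4 bleeding | Drug: "Discontinue modakafusp alfa" |
| Table 8.h | Grade 4 infusion-related reaction | Treatment: "Patient must be withdrawn from treatment" |
| Section 9.4.1 | Adverse event | Drug only; stays for posttreatment assessments |

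Table 8.c therefore changes terms between adjacent rows, and its Grade 4 row differs from the Grade 4 wording for bleeding and infusion-related reactions.

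**2. Is the literal reading open?** Yes. The general text of Section 8.4.3 lists stopping treatment and permanent discontinuation from the study as separate outcomes, and Sections 9.4.1 and 9.4.2 treat them separately. The follow-up sections are in force: Amendment 10 v1, which would have ended PFS and OS follow-up, was not implemented (Protocol Appendix J).

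**3. How direct is each conflict?**

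- PFS: direct. Sections 6.3.1 and 9.4.1 retain anyone who stops without progression, with no exclusion for toxicity.
- OS: weaker. The OS sentences in 6.3.1 and 9.5 end follow-up at patient withdrawal, and 9.4.2 has the residual category. The conflict rests mainly on Section 6.3.4.

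**4. Scheduled visits lost per affected patient.** PFS visits are every 28 days from the end-of-treatment (EOT) visit, which falls 30 to 40 days after last dose, until 6 months (taken as 183 days) after discontinuation. The documents do not say which date counts as discontinuation, so both are tried on nominal dates.

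- Limit counted from last dose, EOT at day 30: days 58, 86, 114, 142, 170 (next would be 198), 5 visits.
- Limit counted from last dose, EOT at day 40: days 68, 96, 124, 152, 180 (next 208), 5 visits.
- Limit counted from the EOT visit: days 28, 56, 84, 112, 140, 168 (next 196), 6 visits.

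The loss is at most 5 to 6 PFS visits, fewer if progression, death or new therapy comes first. The later 12-weekly OS contacts would go as well.

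**5. How many patients meet the row?** The documents give no expected rate. As an assumption only, 5% to 25% of 118 per arm is 118 × 0.05 = 5.9 to 118 × 0.25 = 29.5, about 6 to 30. The upper value is the safety-monitoring limit for treatment-related Grade 4 or higher nonhematologic events. It is not a forecast, and that category includes events that the row excludes. The range counts patients who meet the row's criteria before the exception. Those losing follow-up would be only the ones for whom the exception is not used and the site takes the wording literally.

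**The case against.** The best defence is that the row means stopping drug. The table is headed as dose modification. The exception turns on clinical benefit, which is a reason to stay on treatment and not a natural condition for permitting follow-up visits. The parallel row in Table 8.a goes on to restarting treatment, and Table 8.b and Section 8.4.4 speak of continuing in the study when they mean staying on drug. Sections 6.3.4 and 9.4.1 already settle what happens to patients off treatment. The line beneath Table 8.c requires Part 3 dose modifications to be discussed with the sponsor, and Section 8.4.4 expects the same, with the sponsor or CRO, for discontinuations. A misreading would have to get past both the site and the sponsor.

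Most of this stands. It shows what was probably intended and why misapplication is less likely. It does not remove the conflict: nothing in the row or in those discussion requirements tells a site that follow-up continues once the row is applied.

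Three stronger readings are tempting but unsupported:

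- *The SAP contradicts the row.* It does not. It only depends on data that the literal reading would cut off.
- *OS follow-up is contradicted as plainly as PFS follow-up.* It is not, because the OS text itself stops at patient withdrawal.
- *Unconfirmed partial responses would be lost and the response rate or power reduced.* Responders are the likeliest to fall under the clinical-benefit exception. A footnote to Appendix A Table 13 restricts repeat M-protein and light-chain tests at the EOT visit, but the investigator's response assessment there is unconditional. A sample may also already exist from a planned Day 1 or a delayed cycle. No response-rate or power effect can be derived.

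**Conclusion.** The inconsistency is real and minor. Table 8.c, as worded, conflicts directly with Sections 6.3.1 and 9.4.1 on PFS follow-up and with 6.3.4 on PFS and survival. If followed literally, it would remove post-discontinuation assessments that the SAP uses and make PFS censoring depend on toxicity. PFS, OS and duration of response are descriptive within-arm summaries with no formal comparison of arms, which limits the consequence. Any effect on the response rate or duration of response is confined to responders for whom the exception is not invoked. The number affected is unknown and probably small. Confidence is high that the texts disagree. Whether any site would act on the literal wording is not known.

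**What to change.** Reconcile Table 8.c, Table 8.a and the general text of Section 8.4.3 with Sections 9.4.1, 9.4.2 and 9.5, so that stopping treatment and leaving the study are distinct terms used consistently. Add a sentence that response, PFS and OS follow-up continues under Section 9.5 and Appendix A for patients whose treatment stops because of an adverse event. This takes no view on when treatment should stop.

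The cost is a wording change to the Protocol. The follow-up visits are already scheduled in Appendix A Table 13, and the SAP needs no change.

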8.4.4 Criteria for Discontinuing Modakafusp Alfa

Potential discontinuations of modakafusp alfa should be discussed with the sponsor or contract research organization (CRO) before implementation.

Modakafusp alfa should be discontinued in patients experiencing an AE in Cycle 1 meeting criteria for a DLT for which the investigator considers that retreatment of the patient could be dangerous.

If the next cycle of modakafusp alfa is delayed for >14 days (>28 days for Part 3) because of modakafusp alfa—related toxicities, study treatment should be discontinued unless the investigator considers that the patient will receive benefit continuing in the study. Patients will

be evaluated 30 days (EOT visit) after the last dose of modakafusp alfa or right before the start of subsequent systemic anticancer therapy to permit the detection of any delayed TEAEs.

8.4.5 Dexamethasone Dose Modification

The decision and management of dexamethasone modifications will be according to investigator's discretion. Dose modifications should be recorded in the eCRF.

8.5 Excluded Concomitant Medications and Procedures

The following medications and procedures are prohibited during the study:

- Radiation therapy for disease under study. Local radiotherapy for bone pain is permitted after agreement with the sponsor and once PD is ruled out.
- Any investigational agent other than modakafusp alfa, including agents that are commercially available for indications other than MM that are under investigation for the treatment of MM.
- Concomitant chronic corticosteroid administration of >10 mg of prednisone or equivalent unless given as treatment or prophylaxis for IRRs, as premedication for administration of certain blood products or for exacerbations of respiratory tract disorders, acute pain management, suspected or confirmed immune-mediated thrombocytopenia, or if tumor flare is suspected.

8.6 Permitted Concomitant Medications and Procedures

8.6.1 Premedication

As of Amendment 06, based on the experience with infusion reactions in patients not receiving premedications, it is strongly recommended that all patients receive premedication, including corticosteroids, before modakafusp alfa dosing. Any decision to stop premedications must be discussed with and agreed upon by the sponsor.

Before each injection of modakafusp alfa at doses up to and including 3 mg/kg and for patients receiving a fixed dose in Part 3, patients should receive the following premedications (all or in part) per investigator discretion:

- Corticosteroid IV or orally (PO) (methylprednisolone 100 mg, dexamethasone 20 mg, or equivalent) 60 minutes to 2 hours before treatment; if a patient experiences no significant IRR, the dose of methylprednisolone may be decreased to 50 mg (or dexamethasone to 10 mg) after visit 4. Intermediate- or long-lasting steroids of equivalent dose can be substituted.
- 650 to 1000 mg acetaminophen PO 60 minutes to 2 hours before treatment.
- 25 to 50 mg diphenhydramine or equivalent PO approximately 12 hours before and again approximately 1 hour before Cycle 1 treatment; for all subsequent infusions, approximately 1 hour before.

Montelukast (10 mg PO) may be given to patients who are intolerant to diphenhydramine or for whom diphenhydramine is ineffective.

Patients who are receiving a modakafusp alfa dose of 6 mg/kg or higher must be premedicated with dexamethasone, acetaminophen, diphenhydramine, and montelukast, and it is recommended that the dose will be administered over >2 hours (± 10 minutes). Any decrease in infusion duration must be discussed with and agreed upon by the sponsor.

8.6.2 Postinfusion Medication

Patients may receive 20 to 25 mg prednisone or 4 mg of dexamethasone PO or equivalent on the first and second days after all full-dose infusions. Other concomitant medications can be administered per institutional protocols.

During the infusion and for 2 hours postdose, the patient should be continually monitored by medically qualified staff with access to emergency medical equipment and medications to manage infusion reactions.

8.6.3 Other Permitted Concomitant Medications and Procedures

All necessary supportive care consistent with optimal patient care will be available to patients as necessary. All blood products and concomitant medications will be recorded in the eCRFs as specified in the SOEs (Appendix A).

The following medications and procedures are permitted while the patient is receiving the study drug:

- Myeloid growth factors (eg, granulocyte colony stimulating factor, granulocyte macrophage-colony stimulating factor) and erythropoietin are permitted. Their use should follow the product label, published guidelines, and institutional practice. During Cycle 1, G-CSF is allowed for Grade 4 neutropenia. In addition, G-CSF is allowed to accelerate the recovery of neutropenia to enable the start of new cycle (Section 8.4.2).
- Patients should be transfused with red blood cells and platelets as clinically indicated. Transfusions must be recorded in the concomitant procedure pages of the eCRF. Platelet transfusion should not be applied only for the purpose of meeting the treatment criterion of platelet count to start a new cycle.
- Concomitant treatment with bisphosphonates will be encouraged for all patients with evidence of lytic destruction of bone or with osteopenia, according to the American Society of Clinical Oncology Clinical Practice Guidelines or institutional practice in accordance with the product label, unless specifically contraindicated. If bisphosphonate therapy was not started before the study start, it should be initiated as soon as clinically indicated.
- Topical or inhaled steroids (eg, for the treatment of asthma) are permitted.
- Systemic steroids for acute management of pain, suspected or confirmed immune-mediated thrombocytopenia or other disease or treatment-related complications are permitted.

- Plasmapheresis.
- IV immunoglobulins (IVIG) usage is acceptable for prolonged Grade 4 transfusion-dependent thrombocytopenia or other investigator criteria if it is considered that there is an underlying autoimmune mechanism.
- Thrombopoietin agonists are also allowed for thrombocytopenia management at the investigator's discretion.

